#### **Number of Subjects to be Enrolled:**

Up to 252 subjects are planned to be enrolled and randomly assigned in a 2:1 ratio to receive RBT-9 or placebo (normal saline).

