The interim analyses will be subject to adaptations according to Cui; 2-sided 0.1% alpha at the second (n=60) interim and 2-sided 0.2% alpha at each of the third (n=90) and fourth (n=150) interim analyses. Enrollment will be stopped for futility if the conditional power is <10% based on the percentage of subjects classified in categories 4 through 8 on the 8-point WHO Ordinal Clinical Scale for RBT-9 versus placebo. Enrollment will be recommended if futility is observed. Efficacy will be declared if the conditional power is >80% at the fourth interim analysis; the DSMB will advise regarding study continuation.

**Sample Size Estimate:** The following table summarizes the RBT-9 advantages (15-18%) that can be detected with 84-85% power and 252 subjects for a 2-sided hypothesis test with 5% overall Type 1 error with 2-sided 4.5% Type 1 error remaining at the final analysis; this alpha spend accounts for the preplanned interim analyses.

Two group  $\chi^2$  test: Null hypothesis is Equal Failure %s (odds ratio = 1)

	84-85% Power			Two-sided p=0.045		
	1	2	3	1	2	3
Test significance level, $\alpha$	0.045	0.045	0.045	0.045	0.045	0.045
1 or 2-sided test?	2	2	2	2	2	2
Placebo Failure %, $\pi_1$	25%	32%	38%	25%	32%	38%
RBT Failure %, $\pi_2$	10%	15%	20%	14.6%	20.4%	25.7%
Odds ratio, $\pi_2(1-\pi_1)/[\pi_1(1-\pi_2)]$	0.333	0.375	0.408	0.513	0.545	0.564
Power (%)	84	85	84	NA	NA	NA
Placebo sample size, n1	84	84	84	84	84	84
RBT sample size, n2	168	168	168	168	168	168
Ratio: n2 / n1	2	2	2	2	2	2
N = n1 + n2	252	252	252	252	252	252

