### **9.3 Study Design**

This is a Phase 2, randomized, placebo-controlled, multicenter study that will evaluate the efficacy, tolerability, and safety of a single dose of RBT-9 on the progression of COVID-19 infection in non-critically ill adults who are at high risk due to age and/or comorbid conditions. Subjects with documented SARS-CoV-2 infection who are at high risk for disease progression, as defined in the inclusion criteria (see [Section 9.1](#)), and require observation and/or treatment in a hospital will be screened for entry into the study. Eligible subjects will be stratified by time since COVID-19 diagnosis (<48 hours,  $\geq$ 48 hours) and randomly assigned in a 2:1 ratio to receive a single intravenous infusion of 90 mg RBT-9 or placebo (normal saline). No more than 24 hours can elapse between Screening and Dosing of RBT-9.

All subjects will be assessed through Day 56. All subjects, regardless of hospitalization status, will be assessed on Days 7, 14, 21, and 28, according to the Event Schedule (see [Section 5.1](#)). Assessments will include severity of COVID-19 measured by the 8-point WHO Ordinal Clinical Scale, physical examination, vital signs, clinical laboratory evaluations, concomitant medications, and adverse events. For subjects who have been discharged from the hospital, visits on Days 7, 14, and 21 will be conducted virtually (eg, by telephone or video contact). The Day 28 visit should be conducted in person, but may be conducted virtually, as well. Subjects will also be assessed at safety follow-up visits, which will be conducted virtually (eg, by telephone or video contact) on Days 42 and 56.

An independent data and safety monitoring board (DSMB) will actively monitor interim data to make recommendations regarding study conduct/continuation. The DSMB will meet once the first 30 subjects complete the Day 7 assessment to perform the first interim analysis of the safety data. Enrollment of 30 additional subjects will proceed if the safety profile of RBT-9 is deemed acceptable (as determined by the DSMB). Two additional DSMB interim analyses will be performed once 60 and 90 subjects complete the Day 7 evaluation. The last DSMB interim analysis will be performed once 150 subjects complete the Day 28 evaluation; sample size re-estimation will also be performed to allow a sample size increase to 252 subjects based on pre-defined conditional power rules.

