#### **11.6 Sample Size Calculations**

The following table summarizes the RBT-9 advantages (15-18%) that can be detected with 84-85% power and 252 subjects for a 2-sided hypothesis test with 5% overall Type 1 error with 2-sided 4.5% Type 1 error remaining at the final analysis; this alpha spend accounts for the preplanned interim analyses.

Two group  $\chi^2$  test: Null hypothesis is Equal Failure %s (odds ratio = 1)

	84-85% Power			Two-sided p=0.045		
	1	2	3	1	2	3
Test significance level, $\alpha$	0.045	0.045	0.045	0.045	0.045	0.045
1 or 2-sided test?	2	2	2	2	2	2
Placebo Failure %, $\pi_1$	25%	32%	38%	25%	32%	38%
RBT Failure %, $\pi_2$	10%	15%	20%	14.6%	20.4%	25.7%
Odds ratio, $\pi_2(1-\pi_1)/[\pi_1(1-\pi_2)]$	0.333	0.375	0.408	0.513	0.545	0.564
Power (%)	84	85	84	NA	NA	NA
Placebo sample size, n1	84	84	84	84	84	84
RBT sample size, n2	168	168	168	168	168	168
Ratio: n2 / n1	2	2	2	2	2	2
N = n1 + n2	252	252	252	252	252	252

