## 11.7 Interim Analysis

A group sequential design will be conducted with 3 pre-planned interim analyses after 30, 60, and 90 subjects complete the Day 7 evaluation and once 150 subjects complete the Day 28 evaluation. At each interim, the DSMB will evaluate an independently conducted analysis in order to assess safety and futility.

The interim analyses will be subject to adaptations according to Cui; 2-sided 0.1% alpha at the second interim and 2-sided 0.2% alpha at each of the third and fourth interim analyses. Enrollment will be stopped if the conditional power is <10% based on the percentage of subjects classified in categories 4 through 8 on the 8-point WHO Ordinal Clinical Scale for RBT-9 versus placebo.

For the second, third, and fourth interim analyses, the conditional power will be assessed. Futility will be declared if the conditional power is <10%, while efficacy will be declared at the fourth interim analysis if the conditional power is >80% (with all subjects followed through Day 28); sample size re-estimation will be performed to increase the sample size to 252 subjects. Enrollment will be recommended if futility is observed. If efficacy is declared, the DSMB will advise regarding study continuation.

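### The only stated power (84-85%) is for a fixed 252 subjects, but 252 is described as the size reached by a conditional-power increase, and no starting size or increase zone is given

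*Combined protocol and SAP*

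**What the plan says.** The power statement in Section 11.6, repeated in the synopsis, refers to "RBT-9 advantages (15-18%) that can be detected with 84-85% power and 252 subjects". The table beneath it uses 84 placebo and 168 RBT-9 subjects in every column. It tests at the level left after interim spending: "5% overall Type 1 error with 2-sided 4.5% Type 1 error remaining at the final analysis".

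Three places describe 252 as something the trial grows to. Section 9.3 says of the 150-subject look that "sample size re-estimation will also be performed to allow a sample size increase to 252 subjects based on pre-defined conditional power rules", and the synopsis uses the same words. Section 11.7 says "sample size re-estimation will be performed to increase the sample size to 252 subjects", which, unlike 9.3, does not make the increase conditional. The synopsis enrolment statement is "Up to 252 subjects are planned to be enrolled".

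No section gives the size before the increase. The only conditional-power thresholds are below 10% (futility, second to fourth interims) and above 80% (efficacy, fourth interim). Neither is said to trigger the increase. Section 11.7 names the Cui method for the adaptations. Section 11 leaves full statistical detail to a separate Statistical Analysis Plan.

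**The concern.** A size reached by an increase cannot also be the size before it. If 252 is the planned size, re-estimation has nothing to increase. If the trial starts smaller, 84-85% describes a fixed 252-subject trial rather than the one in Sections 9.3 and 11.7.

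The missing number also matters during the trial. Conditional power is a projection to a final sample size, so the 10% and 80% rules need one. The Cui weights are fixed from the starting size. The sponsor and the DSMB will rely on the 84-85%, and a null result from a trial that ended below 252 would be judged against a power calculated for a larger one.

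**Working it through.** **Inputs.** From the Section 11.6 table: the row labelled "Placebo Failure" (25, 32, 38%), RBT-9 failure 10, 15, 20%, allocation 84:168, two-sided level 0.045. From the synopsis: "2-sided 0.1% alpha at the second (n=60) interim and 2-sided 0.2% alpha at each of the third (n=90) and fourth (n=150) interim analyses". The spending adds up: 0.001 + 0.002 + 0.002 + 0.045 = 0.050.

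**1. Reproduce the plan's figure.** With p̄ = (π1 + 2π2)/3, SE0 = √[p̄(1−p̄)(1/n1 + 1/n2)], SE1 = √[π1(1−π1)/n1 + π2(1−π2)/n2] and z = 2.0047, power = Φ[(π1 − π2 − z·SE0)/SE1]. For 25% v 10% at 84/168: p̄ = 0.15, SE0 = 0.0477, SE1 = 0.0526, and (0.15 − 2.0047 × 0.0477)/0.0526 ≈ 1.03, so power is 84.9%. The other two scenarios give 85.6% and 84.6%. The plan states 84, 85 and 84%, so its figure is reproduced as fixed-sample power at 252.

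**2. Same formula at smaller final sizes.** The last interim look, 150, is the smallest size compatible with the plan.

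| Final N | 25 v 10% | 32 v 15% | 38 v 20% |
|---|---|---|---|
| 150 | 64.9 | 65.2 | 63.6 |
| 180 | 72.3 | 72.9 | 71.4 |
| 200 | 76.5 | 77.1 | 75.8 |
| 220 | 80.1 | 80.8 | 79.6 |
| 252 | 84.9 | 85.6 | 84.6 |

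**3. Whole-design power, illustrative.** Assumptions not in the documents:
- a starting size N0;
- current-trend conditional power at n = 150, CP = Φ[(Z/√t − 2.0047)/√(1−t)] with t = 150/N0;
- an increase to 252 when CP is 10-80%, otherwise a finish at N0, with no power charged to futility;
- a final test at 0.045;
- a true effect giving 85% power at 252 (expected Z of 2.0047 + 1.0364 = 3.0411 there, and 3.0411 × √(150/252) = 2.346 at n = 150).

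Integrating over Z at n = 150:

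| N0 | Power | Power if CP >80% counts as a win | Trials reaching 252 |
|---|---|---|---|
| 160 | 73% | 74% | 18% |
| 180 | 79% | 80% | 26% |
| 200 | 81% | 83% | 28% |
| 220 | 83% | 85% | 28% |

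Pooled and Cui-weighted final tests agree within 1 point. If instead every trial with CP of at least 10% is increased, 76-90% reach 252 and power stays at about 73-83%.

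**4. The decision rules depend on N0.** Take Z = 1.5 at n = 150. With N0 = 160, t = 0.9375 and CP = Φ[(1.549 − 2.005)/0.25] = 3%, a futility stop. With N0 = 220, t = 0.682 and CP = Φ[(1.817 − 2.005)/0.564] = 37%, and the trial continues. The same data lead to opposite decisions.

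**5. Futility, kept separate.** A simulation used interim success at the stated alphas, binding <10% stops at 60, 90 and 150, the same event rates at Day 7 as at Day 28, and no win for CP >80%. It gives 68-69% for a start of 180 and 73-75% when the size is 252 from the outset. With 252 fixed and no futility stop it gives 85-86%.

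**The case against.** The best defence is that Section 11.6 claims only what it says, power "that can be detected with 84-85% power and 252 subjects for a 2-sided hypothesis test", and that this is right. It makes no claim for the whole design. On this view 252 is the planned maximum and the 150-subject look is a gate for going on to it, loosely worded as an increase. On that reading, with conditional power projected to 252, a stop below 10% at n = 150 and a win above 80%, power is 84.8% (82.9% without that win). The stated figure then roughly holds, apart from futility at n = 60 and 90. Moreover, 9.3 calls the conditional power rules pre-defined, and the separate Statistical Analysis Plan may contain the starting size, the zone and the weights.

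Much of this stands, and it rules out several stronger conclusions a reader might draw:
- **That the true power is certainly below 84-85%.** The gap depends on a number not given and may be nil.
- **That only a minority of trials would reach 252.** This follows from the assumed 10-80% zone. Under another zone, most would.
- **That the plan fails on every reading.** The gated-maximum reading is coherent, although three passages are worded against it.
- **That the Cui adaptation cannot be carried out.** What is shown is that the protocol omits what it needs.
- **That the weights cost material power.** The 102 subjects after the look are 40% of 252 but would carry squared weight 1 − 150/N0, which is 6% at N0 = 160 and 32% at 220. Even so, power moves by less than 1 point.

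The conflict itself remains. Starting size is a basic design parameter, Section 11.6 is where it belongs, and only 252 appears there.

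**Conclusion.** The sizing text and the re-estimation text conflict and must be reconciled. The 84-85% is fixed-sample power at the maximum size and is not shown to be the power of the adaptive design.

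The figures at fixed sizes use only the plan's own rates and level. The whole-design range of 73-83% (74-85% with the 80% rule counted as a win) is illustrative. It rests on starts of 160-220, the assumed zone, current-trend conditional power and no futility loss. Against the stated figure, the shortfall runs from about 0 to 12 points. Binding futility stops would lower power further, but that loss arises even with 252 fixed and is not caused by re-estimation.

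**What to change.** In 9.3, 11.6, 11.7 and the synopsis, choose one:

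- **(a)** State that 252 is the planned size and delete the re-estimation and Cui wording.
- **(b)** Keep re-estimation. State the starting size N0 (above 150, below 252) and the conditional-power zone that triggers the increase. Specify the final test after an increase, with weights √(150/N0) and √(1 − 150/N0).

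Under both, label 84-85% as fixed-sample power at the maximum of 252, and restate power for the whole design as run, including the <10% futility stops. Option (a) alone does not make 84-85% the design's power: with those stops binding at all three looks, it is about 73-75% under the assumptions of step 5. Settle the choice before the first conditional-power look at n = 60, because a starting size chosen after interim data are seen undermines the type I error protection the Cui method is meant to give.

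The cost is wording and one simulation table, with no subjects beyond 252. The stated power will be less favourable.

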## 12 WITHDRAWAL FROM STUDY

Every reasonable effort should be made to maintain protocol compliance and participation in the study. Should a subject withdraw or be prematurely terminated from the study for any reason, the reason for early study withdrawal will be recorded. If withdrawal is the result of a serious adverse reaction, the subject will be followed until the condition has resolved, as determined by the Investigator.

The Investigator or Sponsor may withdraw any subject at any time for medical reasons or for administrative reasons (ie, subjects unable or unwilling to comply with the protocol). If so, the subject will be censored at time of withdrawal and, if possible, a final evaluation (End of Study procedures) will be made. All treated subjects will be included in the safety analyses.

In the unlikely event the Sponsor or FDA should determine it is appropriate to terminate the study early, every effort will be made for transitioning subjects with minimal disruption to the subject and Investigator. The IRB will be notified of termination, and reason(s) and procedures for follow-up of research subjects will be developed by the study physician in consultation with the Sponsor and IRB.

## **13 DATA MANAGEMENT**

The standard procedures for handling and processing records will be followed as per GCP and data management standard operating procedures. A comprehensive Data Management Plan will be developed and approved by the Sponsor.

### **13.1 Database Lock**

The database will be locked in order to protect write access after the following preconditions are fulfilled:

- All data are entered in the database
- All adverse events are recorded to the satisfaction of the Chief Medical Officer
- All data queries have been resolved to the satisfaction of the Lead Biostatistician
- All decisions have been made regarding all protocol violators and population exclusions
- Written authorizations to lock the database are obtained from Clinical Data Management and the Chief Medical Officer.

## **14 ETHICAL CONSIDERATIONS**

### **14.1 Ethical Conduct of the Study**

The study will be conducted in accordance with United States Title 21 CFR and the ICH E6 (R1) Guidelines of GCP. The Declaration of Helsinki and its most recent updates (Fortaleza, Brazil; 2013) will be observed.

The Investigator will provide the Sponsor/designee with documentation of IRB approval of the protocol and the sample informed consent document before the study may begin at the investigative site. The IRB will review the protocol as required.

The Investigator will supply the following to the IRB:

- The current Investigator's Brochure and updates
- Study protocol and amendments
- Informed consent and assent document and updates
- Relevant curricula vitae
- Safety alerts
- Serious adverse reaction reports

The Investigator must provide the following documentation to the Sponsor or designee:

- The IRB original approval of the protocol and the informed consent, and re-approval of the study (annual or semi-annual, per IRB guidelines)
- The IRB approvals of any revisions to the informed consent document or amendments to the protocol
- All other documents that are required by local regulatory authorities

## **14.2 Regulatory Considerations**

After reading the protocol, each Investigator/sub-Investigator will sign a protocol signature page and return a copy of the signed page to the Sponsor/designee, while maintaining the original at the site.

## **14.3 Protocol Amendments and Study Termination**

The IRB must be informed and give approval for any amendments likely to affect the safety of the subjects or the conduct of the study.

The IRB must be advised in writing of the study's completion or early termination and a copy of the notification must be provided to the Sponsor.

## **14.4 Safety Monitoring**

The Sponsor's Medical Monitor will monitor safety data throughout the course of the study. The Sponsor's Drug Safety Department, or their designee, will expedite to the regulatory authorities only the suspected adverse reactions that are product-related and unexpected in accordance with FDA 21 CFR 312, FDA Guidance on Safety Reporting Requirements for INDs, and the ICH E2A guideline.

## **14.5 Quality Control and Quality Assurance**

By signing this protocol, the Sponsor agrees to be responsible for implementing and maintaining quality control and quality assurance systems with written standard operating procedures to ensure that the study is conducted and data are generated, documented, and reported in compliance with the protocol, accepted standards of GCPs, and all applicable federal, state, and local laws, rules and regulations relating to the conduct of the clinical study.

By signing this protocol, the Investigator agrees to conduct the study in an efficient and diligent manner and in conformance with this protocol, generally accepted standards of GCP, and all applicable federal, state, and local laws, rules and regulations relating to the conduct of the clinical study.

The Investigator also agrees to allow monitoring, audits, IRB review and regulatory agency inspection of study-related documents and procedures and provide for direct access to all study-related source data and documents. Investigators will be given notice before a quality assurance audit occurs.

The Investigator shall prepare and maintain complete and accurate study documentation in compliance with GCP standards and applicable federal, state, and local laws, rules and regulations, and promptly submit to the Sponsor all forms and reports required by this

protocol following completion or termination of the clinical study or as otherwise required due to any agreement with the Sponsor.

## **15 GENERAL CONSIDERATIONS**

### **15.1 Discontinuation of the Study**

The Sponsor reserves the right to discontinue this study or the Investigator's participation in this study for safety or administrative reasons at any time.

